### **8.4. Secondary Safety Endpoint**

On a **per-limb basis**, the rate of combined minor venous access site closure-related complications through 30 days post-procedure, attributed directly to the closure method (i.e., “device-related” with no other likely attributable cause):

- Access site-related bleeding requiring greater than 30 minutes of continuous manual compression to achieve initial venous hemostasis;
- Access site-related hematoma > 6 cm documented by ultrasound;
- Late access site-related bleeding (following hospital discharge);
- Ipsilateral deep vein thrombosis, confirmed by ultrasound/imaging;
- Localized access site infection confirmed by culture and sensitivity, treated with intramuscular or oral antibiotics;
- Arteriovenous fistula requiring treatment;
- Arteriovenous fistula not requiring treatment;
- Pseudoaneurysm requiring thrombin injection, fibrin adhesive injection or ultrasound-guided compression;
- Pseudoaneurysm not requiring treatment;
- Access site-related vessel laceration;

- Access site-related wound dehiscence;
- Transient access site-related nerve injury.

## **9. Statistical Considerations**

### ***9.1. Analysis Populations and Data Handling Conventions***

#### **9.1.1. Effectiveness**

According to the Intent-to-Treat (ITT) principle, all randomized subjects will be included in all effectiveness analyses and analyzed according to the randomization treatment assignment, regardless of actual treatment deviations.

#### **9.1.2. Safety**

Safety analysis will be performed according to the actual treatment received. All subjects who receive any portion of the Cardiva VVCS device treatment will be analyzed as a VVCS patient; subjects who receive manual compression control treatment only as randomized will be analyzed as a manual compression patient.

#### **9.1.3. Missing Data**

All efforts will be made to eliminate missing data for the primary effectiveness endpoint of TTA and primary safety endpoint of major access site closure complications. However, should missing data be non-trivial, the primary analyses will be based on complete cases with data and sensitivity analyses will be performed to assess robustness of the primary results. Multiple imputations strategy such as assuming missing at random and control based imputation will be employed for the primary effectiveness endpoint; worst case, best case and tipping point analyses will be performed for primary safety endpoint. Missing data for secondary endpoints will not be imputed by any method.

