#### 7.4.6. Post-Operative

After hemostasis is achieved and confirmed at the required intervals, the access site should be monitored every 15 minutes for the first hour for all subjects.

Post-procedure, record the following information:

- **P2 TIME:** Record the date and time the subject was able to ambulate 20 feet without venous re-bleeding from the access sites.
- **P3 TIME:** Record the date and time the subject was eligible for discharge, based solely on the assessment of the access site, as determined by the medical team (i.e., absence of access site bleeding or obvious complications).
- **P4 TIME:** Record the date and time the subject was discharged from the facility.
- Any medication administered for management of pain or anxiety while the subject is on bedrest will be collected.

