## **7.5. Follow-up at 30 (+/- 7) Days**

Subjects should be present for an in-person office visit  $30 \pm 7$  days following their index procedure. The subject should be queried regarding any complications they experienced after hospital discharge and the status of the access site wounds should be assessed. All subjects will be asked about any lower extremity nerve complaints in both lower limbs (i.e., symptoms, severity) that were not existing prior to the index procedure. These data will be captured in the Case Report Forms.

If a subject cannot attend an office visit for any reason, a telephone follow-up should be completed for safety assessment, however this will be documented as a protocol deviation and the subject's follow-up will be considered incomplete. These subjects will not be withdrawn.

At select sites, a subset of 25 subjects from each treatment arm will have an ultrasound exam of the bilateral femoral access sites performed and a digital image recorded for each limb.

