# **8. Assessment of Effectiveness and Safety**

## **8.1. Primary Effectiveness Endpoint**

**Time to ambulation (TTA):** defined as elapsed time between removal of the final Mid-Bore VVCS device (treatment arm) or removal of the final sheath (control arm), and time when subject stands and walks 20 feet without evidence of venous re-bleeding from the femoral access sites (**Per-patient analysis**).

TTA will be reported in hour (hh): minutes (mm).

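### A subject who never completes the 20-foot walk has no TTA, so the complete-case rule in 9.1.3 drops that subject from a primary analysis that 9.1.1 says includes everyone.

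*Combined protocol and SAP*

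**What the plan says.** The relevant text of the combined protocol and SAP is spread over several sections.

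- Section 9.1.1 applies intention-to-treat to effectiveness: "all randomized subjects will be included in all effectiveness analyses and analyzed according to the randomization treatment assignment".
- Section 9.1.3 sets the missing-data rule for both primary endpoints. If missing data are more than trivial, "the primary analyses will be based on complete cases with data and sensitivity analyses will be performed to assess robustness of the primary results". It gives no threshold for the condition and no method for missing data below it.
- Section 9.1.3 then names the sensitivity analyses. For TTA: "Multiple imputations strategy such as assuming missing at random and control based imputation will be employed for the primary effectiveness endpoint". For safety: "worst case, best case and tipping point analyses will be performed for primary safety endpoint".
- Section 8.1 ends the TTA clock at the "time when subject stands and walks 20 feet without evidence of venous re-bleeding from the femoral access sites". Section 7.4.6 defines the P2 time in the same way: "Record the date and time the subject was able to ambulate 20 feet without venous re-bleeding from the access sites". Table 4 computes TTA as P2 minus the removal time at the final access site.
- Section 9.2.2.1 makes the primary test an ANCOVA on mean TTA, adjusted for 3 versus 4 access sites, at one-sided 0.025.

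No section assigns a value, rank or censoring time to a subject who never reaches P2.

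**The concern.** An ANCOVA on a mean needs a number for every subject. A subject who dies, is transferred or is discharged without a successful walk has no P2, hence no TTA, and a complete-case analysis leaves that subject out. The same happens when missing data are trivial, because no other method is given. Sections 9.1.1 and 9.1.3 therefore cannot both be followed once one such subject exists.

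The reason for the missing value matters more than the lost observation. A clock time that nobody wrote down says little about the treatment. A walk that never happened is close to the worst result the endpoint can register. Removing it makes the arm in which it occurred look better, and the result would still be labelled intention-to-treat. Under Section 3 the TTA test is one of the two conditions for trial success.

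**Working it through.** **1. The plan's own figures.** Section 9.3 gives a control mean of 7.2 h, a VVCS mean of 5.0 h with an outlier or 4.3 h without it, a joint SD of 5.4 h, and 102 subjects per arm. The standard error is 5.4 × √(2/102) = 0.756 h.

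- Difference 2.2 h: 2.2/0.756 = 2.91, power = Φ(2.91 − 1.96) = 0.829 (stated 0.83).
- Difference 2.9 h: 2.9/0.756 = 3.83, power = Φ(3.83 − 1.96) = 0.970 (stated 0.97).

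Both reproduce. They also show how sensitive a mean is here: leaving one extreme subject out or in moves the VVCS mean by 0.7 h and the power by 14 points.

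**2. The loss of numbers is not the problem.** Dropping 5 VVCS subjects lowers the t-test power for 2.2 h only from 0.825 to 0.816.

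**3. The shift in the mean.** The documents give no rate of non-walkers and no time to assign them. Assume that k = 1 to 3 of 102 VVCS subjects never walk, that every control walks, that VVCS walkers have mean 5.0 h and SD 5.4 h, and that each non-walker is carried at 24 h.

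Shift in VVCS mean = k × (24 − 5.0)/102 = 0.186k h.

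| k | Shift (h) | Share of 2.2 h | Difference, all subjects (h) | t, all subjects | t, complete case |
|---|---|---|---|---|---|
| 1 | 0.19 | 8% | 2.01 | 2.59 | 2.90 |
| 2 | 0.37 | 17% | 1.83 | 2.29 | 2.90 |
| 3 | 0.56 | 25% | 1.64 | 2.01 | 2.89 |

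The t values ignore the stratification factor. For k = 3, the VVCS sum of squares is 98 × 5.4² + 99 × (5.0 − 5.56)² + 3 × (24 − 5.56)², about 3,909. The variance is 3,909/101 = 38.7, and the pooled SD is √((38.7 + 29.16)/2) = 5.83. Then t = 1.64/(5.83 × √(2/102)) = 2.01. The complete-case difference is 2.2 h in every row. On these assumptions it would take 102 × 2.2/19 = 11.8, about 12, non-walkers to erase the difference.

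**4. What the planned imputations recover.** If missing-at-random imputation gives a VVCS non-walker the VVCS walkers' mean on average, the shift is zero. If control-based imputation gives the control mean, the shift is k × (7.2 − 5.0)/102 = 0.02 to 0.06 h for k = 1 to 3, or 1 to 3% of 2.2 h.

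**The case against.** The strongest reply is that almost nobody will be affected.

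- Randomization follows the procedure. Section 5.1.2 already excludes anyone who cannot routinely walk 20 feet. Section 5.1.3 excludes complications that may prolong ambulation and anyone the physician thinks should not attempt it.
- Under Section 7.4.6 a subject who re-bleeds after walking is walked again and keeps the later time. Times are still collected when a VVCS site cannot be closed with the device.
- In RESPECT (Tables 1 and 2), TTA and time to hospital discharge have the same counts, 275 and 142, so the counts show nobody with a discharge time but no TTA. The other three of the 278 VASCADE subjects lack every time, for reasons not given.

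This stands as an argument that the number is small. It does not supply a rule for the subject who does occur.

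Second, the bias can go either way. Non-walkers in the control arm would make complete-case analysis unfavourable to VVCS: k = 1 to 3 at 24 h would raise the control mean by k × (24 − 7.2)/102 = 0.16 to 0.49 h. That is true, and the one-sided illustration is an assumption.

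Third, control-based imputation does remove the assumed device benefit for a VVCS subject, and the wording of 9.1.3 leaves the list of methods open. Both are fair. But the imputed time is still that of someone who walked, and the analyses are secondary to the complete-case test.

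Two stronger readings might be inferred, and the documents support neither.

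- *Safety.* Section 7.5 says of a subject reached only by telephone that "follow-up will be considered incomplete", which could be read as dropping that subject, or one with an in-hospital event and a missed visit, from the safety analysis. But the same paragraph has the call made to assess safety and keeps the subject in the study. Section 8.3 counts events through 30 days, Section 14.1 adjudicates all reported major and minor closure-related endpoint complications, and worst-case and tipping-point analyses are planned for this endpoint.
- *A much larger TTA bias.* The 78 h maximum TTA in Table 2 might be used as a non-walker's value. That subject walked, so a complete-case analysis would have kept the time; it says nothing about subjects who never walk.

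**Conclusion.** The point holds for the primary effectiveness analysis only. Sections 9.1.1 and 9.1.3 conflict, and the stated rule removes a subject whose missing TTA is itself a poor outcome. The named imputations do not put that outcome back, and no worst-case or tipping-point analysis is named for TTA. That a non-walker counts as missing is inferred from the definition of TTA, but nothing in the documents provides otherwise.

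The group is narrow: late walkers, re-bleeders who later walk, and converted patients who walk all stay in. With 1 to 3 VVCS non-walkers of 102, none in control, a walkers' mean of 5.0 h and an assigned 24 h, the VVCS mean rises by 0.19 to 0.56 h (8 to 25% of 2.2 h), and the complete-case result shows none of it. The count, the arm and the 24 h are assumptions. This does not show that the trial's conclusion would change; it shows that the rule should be settled before the data are seen.

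**What to change.** Amend 9.1.3 so that it agrees with 9.1.1:

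1. Keep every randomized subject in the primary TTA analysis, however little is missing.
2. Give a subject with no successful walk at least the time from final device or sheath removal to discharge or death.
3. Limit multiple imputation to subjects who walked but whose clock time was lost for clerical reasons.
4. Add a tipping-point or worst-case sensitivity analysis for TTA.
5. Add a rank-based check with non-walkers ranked worst. One long time can dominate a mean, and the value in item 2 is only a lower bound, which is misleadingly short after an early death or transfer.

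The cost is mainly SAP wording. Discharge date and time are already recorded as P4; the hour of an in-hospital death may have to be taken from the hospital record. The rule does change how the primary comparison treats non-walkers, so it should be stated openly as such. If non-walkers occur in the VVCS arm, the price is a less favourable VVCS mean and a larger variance, hence some loss of power. The rule also counts non-walking that has nothing to do with the access site, which the sensitivity analyses should show separately.

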## ***9.2. Statistical Analysis Plan***

Results for roll-in patients will be summarized separately and excluded from formal analysis.

#### **9.2.1. Baseline Subject Characteristics**

Subject demographics, baseline characteristics and medical history will be summarized descriptively by randomized treatment arm. Mean, standard deviation, median, minimum, and maximum will be reported for continuous variables. Frequencies and proportions will be reported for categorical variables.

#### **9.2.2. Effectiveness**

##### **9.2.2.1. Primary Effectiveness (TTA) Analysis**

The primary effectiveness endpoint is time to ambulation (TTA) as defined in Section 7.1. Summary statistics for TTA (mean, standard deviation, median, minimum, and maximum) will be reported for all randomized patients (ITT) and further by the randomization stratification factor

(number of access sites per patient: 3 vs. 4) within each treatment arm. The proportions of Cardiva Mid-Bore VVCS converted to manual compression will also be reported.

The main effectiveness analysis will be based on the mean TTA. The hypotheses are as follows.

- $H_0$ : Cardiva Mid-Bore VVCS mean TTA  $\geq$  manual compression mean TTA
- $H_A$ : Cardiva Mid-Bore VVCS mean TTA  $<$  manual compression mean TTA

An ANCOVA analysis will be performed adjusting for randomization stratification factor, i.e. 3 vs 4 access sites. A 1-sided  $p < 0.025$  by t test favoring the Cardiva Mid-Bore VVCS (i.e. shorter TTA) will be regarded as a successful demonstration of the superiority of the Cardiva Mid-Bore VVCS effectiveness over manual compression.

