**Table 2: RESPECT Efficacy Endpoint Results**

	Total N=420	VASCADE (N=278)	Manual Compression (N=142)	p-value*
Time to Hemostasis (minutes)				
N	275	142		
Mean	4.8	21.4		< 0.0001
Std Deviation	5.4	12.4		
Median	3.0	20.0		< 0.0001
Min	0.6	0.0		
Max	31.6	97.0		
Time to Ambulation (hours)				
N	275	142		
Mean	3.8	5.8		< 0.0001
Std Deviation	5.1	3.1		
Median	3.2	5.2		< 0.0001
Min	1.0	1.7		
Max	78.0	22.8		
Time to Discharge Eligibility (hours)				
N	274	142		
Mean	4.8	6.5		0.001
Std Deviation	6.4	3.3		
Median	3.6	5.7		< 0.0001
Min	1.4	2.2		
Max	78.4	23.2		
Time to Hospital Discharge (hours)				
N	275	142		
Mean	18.3	13.7		0.04
Std Deviation	34.5	9.8		
Median	17.2	13.9		0.94
Min	1.7	2.4		
Max	432.9	55.6		
*p-value from t-test for comparing means and Wilcoxon's test for comparing medians				

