#### 7.4.4. Intra-Operative Randomization

At the end of the catheter-based procedure, with the procedural sheaths in place and under fluoroscopic visualization, an injection of contrast will be made to assess sheath placement and the anatomy of all venous access sites to verify the intra-operative eligibility criteria prior to randomization. These images should be saved and printed/stored with the subject's study records for monitoring purposes.

- Each venous access site must meet all intra-procedural access site-specific criteria for the subject to be eligible.

Once it has been determined that the subject does not meet any of the general intra-operative exclusion criteria, and that none of the venous access sites meet the specific access site exclusion criteria (i.e., all venous access sites must meet all study criteria for the subject to be eligible), then the subject is eligible for randomization.

- Once randomized, every access site will be closed according to the treatment assignment (i.e., either VVCS or manual compression).
- Study data will be captured for each access site, according to the instructions below.
- ***NOTE: Any subject that is randomized is considered to be enrolled, and all peri-procedural study data must be collected under the Intent to Treat principle regardless of deviations from the assigned treatment. For this reason, it is imperative that randomization is not performed until the case is complete and final eligibility criteria are confirmed.***
- ***If the subject is randomized to Mid-Bore VVCS and it is subsequently discovered that one or more of the access sites is not able to be closed (e.g., complication) apply manual compression to the affected access sites and close all eligible access sites using Mid-Bore VVCS. All study data will still be collected for each access site. See Section 4.2 Withdrawal of Subjects.***

At each investigational site, variable block randomizations will be performed separately by number of venotomy sites via EDC access at the conclusion of the index procedure, while the patient is on the table. Randomization will be stratified by 3 vs. 4 access sites, and there will be a 1:1 randomization ratio for Cardiva Mid-Bore VVCS vs. manual compression for access site closure. Refer to the Manual of Operations for instructions on how to randomize a subject.

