#### **Cardiva Mid-Bore VVCS:**

Bed rest for 2 hour minimum to a 2.5 hour maximum, then ambulate if stable. Check groin immediately post ambulation. Re-check groin after 15 minutes to verify status. Any ambulation delay beyond 3 hours final access site hemostasis time that is not related to a medical condition (e.g., pt. is sleeping, no staff available) will be documented, and a Protocol Deviation will be written. NOTE: If one or more of the access sites are not able to be closed with the Mid-Bore VVCS (e.g., complication preventing use of the device, user error), subjects should be maintained on bedrest according to the Investigator's discretion and all study times will be collected. This would not constitute a deviation from the protocol.

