#### **Manual Compression:**

Follow institutional guidelines for ambulation. Check groin immediately post ambulation. Re-check groin after 15 minutes to verify status. Any delays of > 30 minutes beyond institution's standard practice for ambulation that are not related to a medical condition (e.g., pt. is sleeping, no staff available) will be documented, and a Protocol Deviation will be written.

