### **9.3. Sample Size Justification**

#### Effectiveness

Based on a prior study (RESPECT), mean TTA for manual control is estimated at 7.2 hours. The same mean for Cardiva Mid-Bore VVCS is estimated at 5 hours including an outlier and at 4.3 hours excluding the outlier. With an estimated joint standard deviation of 5.4 hours, the power for reaching a statistically significant difference at 2-sided 0.05 level with a total sample size of 204 (102 per group) is 0.83 including the outlier in the calculation; the same power is 0.97 excluding the outlier.

Safety

For the purpose of sample size/power estimation, we will assume major access site closure complications to be independent between the two limbs of the same subject. Based on clinical experience this is the most likely scenario for these rare events. According to review of the VASCADE arterial VCS RESPECT study, the combined major complication rate by limb is estimated to be 2% for both VVCS and manual compression. With these assumptions, simulations were conducted using the R software for a sample size of 204 each for VVCS and manual compression patients. The power for the Newcombe 2-side 95% confidence upper limit to exclude 5% is approximately 0.88.

In order to evaluate the Newcombe method as an approximation to the proposed analysis method, i.e. bootstrap by patient, systematic comparisons were performed between the upper limit of Newcombe and bootstrap confidence intervals. Complication rates of 0% – 3% were selected for comparison, as this range is expected to cover great majority of the actual cases. The results are presented in the following table.

 IDE G100246

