#### **9.4. Planned Interim Analysis**

An interim analysis in support of a CE Mark submission will be conducted to analyze initial subjects randomized to the treatment arm only with respect to efficacy and safety. This interim analysis is not intended to support a decision to continue or to discontinue the trial, or to implement any modifications to trial procedures.

To alleviate potential statistical and operational bias that may be introduced, the execution of the interim analysis shall be a completely confidential process to the study team. All sponsor staff, staff contracted by the sponsor, and investigator staff directly involved in the conduct of the ongoing IDE trial will remain blind to the process and results of the analyses, with the exception of contracted resources involved in the execution of the interim analysis and submission of the results on behalf of the sponsor.

Endpoints to be evaluated using descriptive statistics are as follows:

- Primary efficacy: Time to Ambulation
- Secondary efficacy: Total Post Procedure Time, Time to Hemostasis, Time to Discharge Eligibility, Time to Discharge
- Primary safety: rate of major complications related to the access site
- Secondary safety: rate of minor complications related to the access site

In addition, device success and procedure success will be evaluated, as well as patient experience survey data.

Randomization: This is a single-arm analysis, therefore subjects randomized to control arm will be excluded.

Sample Size: 30-40 sequential subjects randomized to treatment arm from up to 7 centers.

A final clinical report will be prepared at the conclusion of the interim analysis by an agent of the sponsor who is independent from the conduct of the study. The report will be unblinded following the collection of the last patient's procedure data.

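### Randomization is blocked within investigational site, but the primary TTA model omits site: the test is not anti-conservative for the participating sites, though its SE may be somewhat too wide (optional, low-cost change)

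*Combined protocol and SAP*

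**What the plan says.** Section 7.4.4 describes the allocation: "At each investigational site, variable block randomizations will be performed separately by number of venotomy sites via EDC access". Both investigational site and number of access sites (3 or 4) therefore define the blocks. Sections 4.2 and 7.2, and section 7.4.4 itself, name only 3 vs 4 access sites as the stratification factor.

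The primary effectiveness model in section 9.2.2.1 follows that naming: "An ANCOVA analysis will be performed adjusting for randomization stratification factor, i.e. 3 vs 4 access sites". Success is a 1-sided p below 0.025. Section 9 gives no investigational-site term, site-adjusted sensitivity analysis or pooling rule for TTA. Section 4.3 allows 8 to 20 sites, none with more than 25% of the pivotal subjects.

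Two other parts bear on how far TTA may differ between sites. In section 7.4.6 the device arm has one rule everywhere, "Bed rest for 2 hour minimum to a 2.5 hour maximum, then ambulate if stable", and the control arm is told "Follow institutional guidelines for ambulation". Section 9.4 plans an interim look "to analyze initial subjects randomized to the treatment arm only with respect to efficacy and safety".

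**The concern.** Blocking within site balances the arms at each site, so a TTA level common to both arms of a site largely cancels from the treatment difference. The true variance of the estimate falls. A model without site does not register this: the between-site variation stays in the residual, so the SE is overstated, the confidence interval is too wide and the p-value is too large. Section 9.2.2.1 adjusts for the factor used in randomization but leaves out the other factor that defines the blocks. At stake is some efficiency in the reported inference, and a match between that inference and the design as run. The point estimate itself loses essentially nothing, because blocking already balances site.

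**Working it through.** **Inputs from the plan.** Section 9.3: control mean 7.2 h; device mean 5 h with an outlier and 4.3 h without, so the difference δ is 2.2 h or 2.9 h; SD 5.4 h; 102 per arm; stated power 0.83 and 0.97. Section 4.3: 8 to 20 sites.

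**Assumption.** The between-site share ρ of TTA variance is not in the documents. Shares of 5%, 10% and 20% correspond to site SDs of 5.4 × √ρ = 1.2, 1.7 and 2.4 h.

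**Step 1: the plan's own figure.** SE = 5.4 × √(2/102) = 0.756 h. Normal-approximation power Φ(2.2/0.756 − 1.96) = 0.829, and 0.970 at 2.9 h. The non-central t gives 0.825 and 0.968. The stated power reproduces.

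**Step 2: shared site level, by formula.** With perfect balance within site, the true SE is 0.756 × √(1 − ρ), while the model without site still reports about 0.756. At ρ = 0.10:
- true SE = 0.756 × √0.90 = 0.717 h;
- 1-sided error = 1 − Φ(1.96 × 0.756/0.717) = 0.019;
- power without site at 2.2 h = Φ((2.2 − 1.96 × 0.756)/0.717) = 0.842;
- power with site = Φ(2.2/0.717 − 1.96) = 0.866.

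At 2.9 h the same formulas give gains from adding site of 0.3, 0.5 and 0.8 points at shares of 5%, 10% and 20%.

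**Step 3: simulation with incomplete blocks and unequal sites.** There were 20,000 trials per setting: 204 subjects, δ = 2.2 h, total SD 5.4 h in each arm, blocks of 2 and 4 within site and 3-vs-4 stratum (half of patients assumed in each), and 8, 16 or 20 sites, none above 25%. Site effects were centred over the participating sites. Monte Carlo error of each power change is at most 0.16 points. Pooled means that sites with fewer than 8 subjects form one group. Ranges run over the three numbers of sites.

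| Shared share | Reported SE, planned model (h) | True SD of estimate (h) | 1-sided error | Power change from adding site (points) | Same, small sites pooled |
|---|---|---|---|---|---|
| 5% | 0.753–0.754 | 0.735–0.745 | 0.023 | +0.3 to +1.0 | +0.65 to +0.95 |
| 10% | 0.750–0.753 | 0.719–0.727 | 0.021 | +1.5 to +2.0 | +1.5 to +2.0 |
| 20% | 0.743–0.750 | 0.683–0.691 | 0.017–0.018 | +3.9 to +4.3 | +3.4 to +3.9 |

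At 16 sites and 10%, power goes from 0.840 to 0.858. A separate run of 3,000 null trials at 10% gave a true SD of 0.708 h (8 sites) and 0.725 h (20 sites), with 1-sided error 0.017 and 0.018. The SD of the point estimate differs between the two models by at most 0.008 h in every setting.

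**Step 4: site differences mainly among controls.** With site SD 1 to 2 h in controls and 0.25 to 0.5 h in the device arm, the change in power is −0.7 to +0.9 points (pooled −0.1 to +0.9). With control-only SD of 1 to 3 h it is −0.9 to +1.5 (pooled −0.2 to +1.5).

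**Step 5: no site differences.** Adding site changes power by −0.1, −0.6 and −1.1 points at 8, 16 and 20 sites (pooled −0.1, −0.3 and −0.5).

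**The case against.** The strongest reply is that nothing here is an error. Leaving centre out of an ANCOVA is a legitimate pre-specified choice, the plan names 3 vs 4 access sites consistently as its stratification factor, and the model adjusts for exactly that. This stands, and it is why the change is optional.

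The second reply is that the documents point towards the setting where a site term does least. The device arm has a common bed-rest window, and the protocol treats as a deviation "Any ambulation delay beyond 3 hours final access site hemostasis time that is not related to a medical condition". Controls follow each institution's practice. Site differences would then sit mainly in one arm, where a site main effect recovers little. This also stands; Step 4 gives the size. The 2.9 h scenario in section 9.3 likewise leaves under 1 point to gain even at a 20% share.

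It is tempting to go further and argue from "Table 2: RESPECT Efficacy Endpoint Results" that any shared site variance must be small. Removing the single 78 h maximum from the device arm (n 275, mean 3.8 h, SD 5.1 h) leaves a mean of (275 × 3.8 − 78)/274 = 3.5 h and an SD of about 2.4 h. The result does not carry over to the planning figures. Section 9.3 states: "The same mean for Cardiva Mid-Bore VVCS is estimated at 5 hours including an outlier and at 4.3 hours excluding the outlier". That is a shift of 0.7 h, against 0.3 h in Table 2, and the control means are 7.2 h and 5.8 h. The two sets of figures do not describe the same arms, so the size of a shared site component remains unknown.

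**Conclusion.** The mismatch between sections 7.4.4 and 9.2.2.1 is real, and its consequence is minor. It makes the reported SE too wide only to the extent that sites share a TTA level across arms. At an assumed 10% share and 2.2 h, adding site is worth about 1.5 to 2 points of power; in the control-dominated case it is worth about 0 to 1 point. Every between-site figure is an assumption.

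Three stronger readings are not supported:

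- A reader might infer that omitting a blocking factor biases the estimate, inflates type I error or leaves the trial short of its stated power. For the participating sites the error moves below 0.025, not above it, and 0.83 reproduces.
- A reader might take the 20% row (about 4 points) as the expected loss. Nothing in the documents supports a share of that size.
- A reader might take the test to be conservative for any wider population of sites. That holds only for the participating sites, or if there is no effect at any site. If sites are regarded as a random sample and control practice alone varies, at an extreme assumed share of 30% in controls, 1-sided rejection was about 0.14 to 0.15 with 8 sites and 0.08 with 20, with or without a site term. Treatment effects that vary across sites are a separate question, which this change does not address.

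**What to change.** Optional, and best settled in advance:

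- In section 9.2.2.1, add investigational site as a fixed effect in the primary TTA ANCOVA, alongside 3 vs 4 access sites, and mention the within-site blocking of section 7.4.4.
- State a rule for pooling small sites. Fewer than 8 randomized subjects was the threshold used above and is only illustrative.
- Fix model and rule before the section 9.4 interim analysis. That analysis summarizes treatment-arm TTA, and a site model or pooling rule chosen afterwards could be challenged as data-driven.

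The cost is one line of wording, a pooling rule and up to 19 of about 200 degrees of freedom, with no new data or patients. If sites do not differ, the loss is about 0.5 points of power with small sites pooled and about 1 point at 20 unpooled sites.
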